9.1.1.1 Replacement policy

Subjects who were randomized, but not dosed may be replaced.

9.1.2 Withdrawal of informed consent and exercise of participants' data privacy rights

Withdrawal of consent/opposition to use of data and/or biological samples occurs in countries where the legal justification to collect and process the data is consent and when a subject:

- Explicitly requests to stop use of their data
and
- No longer wishes to receive study treatment
and
- Does not want any further visits or assessments (including further study-related contacts)

This request should be as per local regulations (*e.g.* in writing) and recorded in the source documentation.

Withdrawal of consent impacts ability to further contact the participant, collect follow-up data (*e.g.* to respond to data queries) and potentially other country-specific restrictions. It is therefore very important to ensure accurate recording of withdrawal vs. discontinuation based on the protocol definitions of these terms.

In this situation, the investigator should make a reasonable effort (*e.g.* telephone, e-mail, letter) to understand the primary reason for the subject's decision to withdraw their consent/exercise data privacy rights and record this information. The Investigator shall clearly document if the subject has withdrawn his/her consent for the use of data in addition to a study discontinuation.

Study treatment must be discontinued and no further assessments conducted, and the data that would have been collected at subsequent visits will be considered missing.

Further attempts to contact the subject are not allowed unless safety findings require communicating or follow-up. If the subject agrees, a final evaluation at the time of the subject's withdrawal of consent/exercise data privacy rights should be made as detailed in the assessment table ([Table 8-1](#)).

Further details on withdrawal of consent or the exercise of subjects' data privacy rights are included in the corresponding informed consent form.

9.1.3 Lost to follow-up

For subjects whose status is unclear because they fail to appear for study visits without stating an intention to discontinue or withdraw, the investigator must show "due diligence" by documenting in the source documents steps taken to contact the subject, *e.g.* dates of telephone calls, registered letters, etc. A subject should not be considered as lost to follow-up until due diligence has been completed.

9.1.4 Study stopping rules

The Sponsor, the DMC and Lead Investigator will continually review and *ad hoc* as needed, adverse events and laboratory findings throughout the study, including the number and/or severity of adverse events, cumulative cases of clinically significant adverse events, severe adverse events, clinically significant laboratory changes, except those that are reasonably suspected to be due to extraneous causes.

As a result of the safety review, study recruitment or the study (a part/ or cohort of the study) may be placed on hold pending further safety analysis if Novartis, the DMC, and Lead Investigator, considers that the cumulative number and/or severity of AEs or other clinically significant changes are deemed unsafe to continue recruitment or dosing. Novartis and the Lead Investigator must jointly evaluate the relationship between an adverse event and CFZ533, and decide whether to resume enrollment, or to stop one cohort, all dosing, or to terminate the study prematurely.

Study recruitment will be stopped, pending a full safety review, if any of the following criteria are met:

- At least 2 of the 6 (for Cohort 1) or 3 of the 10 (for Cohort 2) subjects in the same cohort experience a CFZ533-related AE (CTCAE grade 3 or higher) in the first month of treatment.
- Three (3) or more subjects with recurrent and severe systemic infections (CTCAE grade 3) per cohort in the first month of treatment, or more than 50% of all treated subjects at any point in time.
- One (1) or more subjects with a severe allergic reaction (CTCAE grade 3 or higher) to study drug in the first five (5) treated subjects or an incidence of > 20 % thereafter.
- One (1) or more subjects with cytokine release syndrome.
- The sponsor unilaterally requests it.
- The DMC recommends it.

If one of the above stopping rules is met, the Competent Authorities and Institutional Review Board/Independent Ethics Committee (IRB/IEC) will be informed of the temporary halt of study via a Substantial Amendment in accord with local regulations. The study may resume following the safety review, if the Sponsor and DMC, and Lead Investigator agree it is safe to proceed and after approval to restart the study is obtained from the Competent Authorities and IRB/IECs.

Cohort stopping rules are described in the above study stopping criteria list.

Individual stopping rules are listed in the [Section 9.1.1](#).

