T1DM patients are not immunosuppressed and the data generated to date in healthy volunteers, and in patients with no or minimal immunosuppression, such as Primary Sjögren's Syndrome are likely to be more relevant: such data also do not suggest an increased infection risk. However, as data are limited, no definitive conclusions can be made and infection remains an important risk for CFZ533 and will be mitigated in the proposed trial.

In autoimmune diseases under investigation, to date,

CCI

which can be seen in hyperimmunoglobulin M syndrome, a rare disorder of CD154 (CD40 ligand (CD40L)) deficiency characterized by defective class-switch recombination (CSR), resulting in normal or increased levels of serum IgM associated with deficiency of immunoglobulin G (IgG), immunoglobulin A (IgA), and immunoglobulin E (IgE) and poor antibody function.

Potential risk associated with SARS-CoV-2 (COVID-19)

Novartis is committed to supporting the safety and well-being of our study participants, investigators, and site staff. All local regulations and site requirements must be applied in the countries that are affected by the COVID-19 pandemic. Having T1DM does not make patients more susceptible to contracting COVID-19, but the disease may be more severe in patients with diabetes than in those without ([CDC 2020](#)). This is largely driven by obesity and type 2 diabetes and there is no current evidence that younger individuals with type 1 diabetes are at increased risk for more severe disease ([CDC 2020](#)).

SARS-CoV-2 Vaccination

Study subjects are not specifically mandated to receive COVID-19 vaccination prior to study entry. However, subjects must complete all locally recommended immunizations, including COVID-19 vaccinations where applicable, prior to first dose with study drug and in accordance with local immunization guidelines. Killed/inactive vaccines must be administered at least 2 weeks prior to first dose with study drug. Currently, there are no live, attenuated COVID-19 vaccinations available, but this may be subject to change if new vaccine types are developed. Investigators must be sure to check locally approved vaccine types. Immunization with a live, attenuated vaccine must be completed at least 8 weeks prior to the first dose. Administration of live, attenuated vaccines during treatment is prohibited and should be avoided while receiving CFZ533 (iscalimab) and for at least CCI thereafter.

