8.3.1 Hypoglycemic events

The American Diabetes Association (ADA) has proposed a definition of hypoglycemia as an event accompanied by a measured plasma glucose concentration ≤ 3.9 mmol/L (70 mg/dL) based on the observed threshold for glucose counter-regulation activation in a non-diabetic population with a lower threshold of 3.9 mmol/L (70 mg/dL) as the definition of clinically relevant glucose levels ([Workgroup on Hypoglycemia, American Diabetes Association 2005](#); [Sequist et al 2013](#)).

While standardized reporting of hypoglycemia is desirable, it has been argued that defining hypoglycemia at a glucose level ≤ 3.9 mmol/L (70 mg/dL) may lead to considerable overestimation of the frequency of clinically relevant hypoglycemia. In a study report with a large cohort of patients it was shown that a threshold level of 3.1 mmol/L (56 mg/dL) would provide a more accurate estimate of the frequency ([Swinnen et al 2009](#)) Continuous glucose monitor (Dexcom) alert and alarm thresholds are set at 54 mg/dL (3.0 mmol/L) and so this proposed cut-off value will be used in the current study to define hypoglycemia events.

Severe hypoglycemia is an event requiring assistance of another person to actively administer carbohydrates, glucagon, or take other corrective actions.

Hypoglycemic data will be classified as defined in [Table 8-3](#). Glycemic thresholds above and below 54 mg/dL (3.0 mmol/L) indicate different degrees of urgency for clinical action: Hypoglycemia with glucose 54 to 69 mg/dL (3.0 to 3.9 mmol/L, often referred to as Level 1 hypoglycemia), is an alert threshold, independent of any acute symptoms, and healthcare professionals and people with diabetes should monitor time spent in this range of hypoglycemia. Hypoglycemia with a glucose level of below 54 mg/dL (3.0 mmol/L, often referred to as Level 2 hypoglycemia), with or without symptoms, is considered clinically significant in that it may trigger counterregulatory responses, cause cognitive impairment leading to severe hypoglycemia, and therefore requires immediate attention.

While hypoglycemic adverse events will follow the classification in [Table 8-3](#), adverse events other than hypoglycemia will follow standard grading mild, moderate, or severe ([Section 10.1.1](#)) grading system.

Hypoglycemia events will be recorded in the study diary which will be reviewed and discussed with the subject at each visit. Hypoglycemia may also be assessed via CCI

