9.1 Discontinuation

9.1.1 Discontinuation of study treatment

Discontinuation of study treatment for a subject occurs when study treatment is stopped earlier than the protocol planned duration, and can be initiated by either the subject, the investigator, or the Sponsor.

The investigator must discontinue study treatment for a given subject if, he/she believes that continuation would negatively impact the subject's well-being.

Study treatment must be discontinued under the following circumstances:

- Subject/guardian decision
- Informed consent/assent is withdrawn
- Pregnancy
- Use of prohibited treatment as per recommendations in the prohibited treatment section (see [Section 6.2.2](#))
- Any situation in which study participation might result in a safety risk to the subject
- Following emergency unblinding

Subjects may voluntarily discontinue the study for any reason at any time.

Missing CCI will drop systemic drug levels below concentrations which can be expected to provide clinical efficacy. Subjects should therefore not miss more than 2 subsequent doses of study drug in CCI . Similarly, 2 consecutive doses cannot be missed more than once within a CCI period as this would also drop systemic levels below concentrations which can be expected to provide clinical efficacy. Subjects who have missed 3 or more doses in CCI or have missed 2 consecutive doses more than once within CCI will need to discontinue treatment permanently. The site should contact Novartis for further guidance if multiple compensatory doses are required.

Site Investigators should discontinue or temporarily suspend study treatment for any given subject if, on balance, they believe that continuation would be detrimental to the subject's well-being. Site Investigators should contact Novartis prior to resuming study drug that was discontinued or temporarily suspended for safety reasons. The DMC may be involved in the decision to resume dosing.

Study treatment must be discontinued and medical treatment must be started per standard of care where needed at the site Investigator's discretion under the following circumstances:

- Infusion reactions/anaphylaxis reactions to CFZ533.
- Recurrent systemic or severe infections. Recurrent local candidiasis, *e.g.* genital that is responsive to topical standard of care treatment and is deemed related to inadequate glycemic control is exempt.

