- Severe infections. Resumption of dosing may be considered once the course of anti-infective therapy is completed and the infection is documented as cleared, so long as 3 or more doses have not been missed. For COVID-19, clearance of infection in order to resume treatment during the study requires resolution of symptoms and absence of infectious virus / viral replication from a respiratory specimen.
- Neutropenia with an absolute neutrophil count (ANC) $< 0.5 \times 10^9/L$ until resolution defined as an ANC $> 1 \times 10^9/L$ on 2 separate occasions.
- Severe and symptomatic hypogammaglobulinemia, *e.g.* IgG levels lower than 400 mg/dL necessitating replacement therapy with gamma globulins.

Resumption of dosing for subjects in whom study treatment was temporarily suspended must be decided based on the site Investigator's judgement, in consultation with the Sponsor and the DMC on a case-by case basis.

If permanent discontinuation of study treatment occurs, the investigator should make a reasonable effort to understand the primary reason for the subject's premature discontinuation of study treatment and record this information.

Subjects who discontinue study treatment or who decide they do not wish to participate in the study further should NOT be considered withdrawn from the study UNLESS they withdraw their consent/assent (see [Section 9.1.2](#) withdraw of informed consent section). Where possible, they should return for the assessments indicated in the assessment schedule. If they fail to return for these assessments for unknown reasons, every effort (*e.g.* telephone, e-mail, letter) should be made to contact the subject/pre-designated contact as specified in the lost to follow-up section (see [Section 9.1.3](#)). This contact should preferably be done according to the study visit schedule.

If the subject cannot or is unwilling to attend any visit(s), the site staff should maintain regular telephone contact with the subject, or with a person pre-designated by the subject. This telephone contact should preferably be done according to the study visit schedule.

After study treatment discontinuation, at a minimum, in abbreviated visits, the following data should be collected at clinic visits or via telephone/email contact:

- new / concomitant treatments
- Adverse Events/Serious Adverse Events

The investigator must also contact the IRT to register the subject's discontinuation from study treatment.

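### The infection halting rule is capped at CTCAE grade 3, so read literally it stops counting subjects when their infections become more severe

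*Protocol*

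**What the plan says.** Section 9.1.4 of the protocol lists criteria that stop recruitment pending a full safety review. Three of them carry a CTCAE grade:

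- Related events: at least 2 of 6 subjects in Cohort 1, or 3 of 10 in Cohort 2, who "experience a CFZ533-related AE (CTCAE grade 3 or higher) in the first month of treatment".
- Infections: the month-1 limb needs a minimum of three affected subjects, the event being "recurrent and severe systemic infections (CTCAE grade 3) per cohort in the first month of treatment". A second limb of the same trigger has no time window and applies to the whole treated group: "or more than 50% of all treated subjects at any point in time".
- Allergic reactions: one or more of the first five treated subjects with "a severe allergic reaction (CTCAE grade 3 or higher) to study drug", or an incidence above 20% thereafter.

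The remaining criteria are any case of cytokine release syndrome, a sponsor request and a DMC recommendation. The SAP does not restate or amend these rules.

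Section 4.5 states that "infection remains an important risk for CFZ533 and will be mitigated in the proposed trial", names stopping rules among the means of controlling risk, and notes that this is the first pediatric study of the antibody.

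**The concern.** Two of the three graded triggers have an open upper end and the infection trigger does not. The word 'severe' does not settle the matter, because the allergic-reaction trigger also says 'severe' and still adds 'or higher'. A reader applying the list as printed could take the difference as intended.

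The infection trigger is also the only numeric infection criterion that does not depend on causality. The related-event trigger needs an attribution to CFZ533, and an unrelated call is plausible here: Section 4.5 says that some infection risk in children goes with their age group whatever their immune competence, and the discretionary review in Section 9.1.4 sets aside events thought to have extraneous causes. Infections attributed elsewhere are therefore the ones this trigger has to catch, and at grade 4 or above it would not catch them.

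At stake is whether a mandatory pause in recruitment of adolescents and young adults follows from the most serious infections or depends on someone's discretion.

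**Working it through.** The documents give no operating characteristics for the stopping rules, so there is no stated figure to reproduce. The check applies the printed rule and the edited rule to the same cases.

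Inputs, all from Section 9.1.4 unless noted:

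- Infection trigger: at least 3 subjects per cohort in month 1, no relatedness condition.
- Related-event trigger: grade 3 or above, related only, month 1 only; 2 subjects needed in Cohort 1, 3 in Cohort 2.
- Later infection limb: more than half of all treated subjects.
- Planned size: 44 (Section 3).

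Simplification: each subject is given one grade for all of his or her recurrent systemic infections.

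**Step 1. Infection trigger, month 1, one cohort, three affected subjects.** Count as printed = subjects at exactly grade 3. Count as edited = subjects at grade 3 or above. Halt if the count is at least 3.

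| Grades | Count as printed | Count as edited | Trigger met as printed | Trigger met as edited |
|---|---|---|---|---|
| 3, 3, 3 | 3 | 3 | yes | yes |
| 3, 3, 4 | 2 | 3 | no | yes |
| 4, 4, 4 | 0 | 3 | no | yes |

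**Step 2. Add the related-event trigger.** Let k of the three subjects have events judged related, with no other related event of grade 3 or above. Cohort 1 halts when k ≥ 2; Cohort 2 halts when k ≥ 3. For grades (3, 3, 4) and (4, 4, 4) the edit therefore changes the outcome at:

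- Cohort 1: k = 0 or 1.
- Cohort 2: k = 0, 1 or 2.

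Above those values recruitment stops under either wording.

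**Step 3. After month 1.** The related-event trigger no longer applies, and only the limb based on all treated subjects remains for infections. With all 44 treated, 22/44 = 50.0% does not exceed one half and 23/44 = 52.3% does, so 23 subjects are needed. The edit will rarely decide anything there.

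**Step 4. Illustration with assumed rates (none are in the documents).** Suppose 10 subjects each have probability 0.20 of a qualifying infection of grade 3 or above, and a share s of those is grade 4 or 5. The probability that the infection trigger alone reaches 3 is P(X ≥ 3), with X binomial(10, 0.20) as edited and binomial(10, 0.20 × (1 − s)) as printed:

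- As edited: 0.32.
- As printed, s = 10%: 0.26; s = 25%: 0.18; s = 50%: 0.07.

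With probability 0.10 in place of 0.20, the edited value is 0.07 and the printed values are 0.05, 0.03 and 0.01. This shows only how far the one trigger loses sensitivity. It does not give the chance that a halt is missed, because the related-event trigger and the discretionary halts are left out.

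**The case against.** The strongest reply is that the parenthesis merely explains 'severe' and sets a floor. Reading it as exactly grade 3 would make a life-threatening infection not severe, which no sensible DMC would accept. That is very likely the intent, but the neighboring triggers spell the floor out and this one does not, so the text leaves room for the other reading.

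Second, routine severity recording cannot make the distinction: "adverse events other than hypoglycemia will follow standard grading mild, moderate, or severe", and Section 10.1.1 has nothing above severe. This stands as a limit. The gap opens only where someone assigns a CTCAE grade at the safety review and applies the parenthesis as written. All three graded triggers, however, need that grade to be assigned.

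Third, the scenario is remote. It needs three subjects in one cohort, each with recurrent systemic infections of grade 3 or above within a month, few of them judged related. This also stands. A single grade 4 infection in a subject would not count even after the edit, since the trigger requires recurrence. A grade 5 event can only be the last in a series. A subject with infections of mixed grade is not clearly classified by the printed rule.

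Fourth, there are backstops. A DMC recommendation or a sponsor request also stops recruitment, SAEs reach the sponsor within 24 hours whatever their cause (Section 10.1.3), and Section 9.1.1 requires individual discontinuation for "Recurrent systemic or severe infections", with a further entry that begins "Severe infections. Resumption of dosing may be considered once the course of anti-infective therapy is completed". Neither entry has an upper grade limit. These protections are real and reduce the likely harm. Even so, they are discretionary, informational or confined to one subject, and none is a numeric halt for the study.

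**Conclusion.** The concern holds. As printed, the infection trigger excludes subjects above grade 3. In month 1 such infections lead to a numeric halt only through the related-event trigger. With three affected subjects, at least one of them at grade 4, the wording decides the outcome when at most one is judged related in Cohort 1 or at most two in Cohort 2.

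This rests on a literal reading, on CTCAE grades being assigned at the review, and on no other related event of grade 3 or above in that month. The practical reach is small: the infections must be recurrent, the edit hardly matters after month 1, and it has value only while recruitment is open, which the documents do not state. It should still be corrected, because this is the operative threshold of a mandatory safety rule for a risk the protocol itself calls important, and no rationale is offered for an upper limit.

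**What to change.** In the infection bullet of Section 9.1.4, add 'or higher' after the CTCAE grade, to match the related-event and allergic-reaction bullets. The number of subjects, the one-month window and the one-half limb stay as they are.

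The cost is two words, which can go into the next amendment, and a slightly readier pause in recruitment. If grade 3 and above was always meant, the edit only makes the text say so.

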9.1.5 Early study termination by the sponsor

The study can be terminated by Novartis at any time.

Reasons for early termination:

- Unexpected, significant, or unacceptable safety risk assessment of participating to subjects enrolled in the study, practical reasons (including slow enrollment), or for regulatory or medical reasons.

- Decision based on recommendations from applicable board(s) after review of safety and efficacy data.
- Discontinuation of study drug development.

In taking the decision to terminate, Novartis will always consider the subject welfare and safety. Should early termination be necessary, subjects must be seen as soon as possible (provide instruction for contacting the subject, when the subject should stop taking drug, when the subject should come for a final visit) and treated as a prematurely withdrawn subject. The investigator may be informed of additional procedures to be followed in order to ensure that adequate consideration is given to the protection of the subject's interests. The investigator or sponsor depending on the local regulation will be responsible for informing IRBs/IECs of the early termination of the trial.

